The aim of the study is to evaluate the effect of administering a normo/hypocaloric Mediterranean diet regimen on body composition in pediatric children, after 3 and 6 months from the start of the diet. Specifically, we want to evaluate the body composition of children and adolescents with overweight and obesity with respect to adherence to a dietary regimen, according to clinical practice. In particular, we want to evaluate the effect of administration of a normo/hypocaloric Mediterranean diet regimen on pediatric body composition.

MATERIALS AND METHODS

All children and adolescents who come to the SCDU of Pediatrics, Outpatient Endocrinology and Auxology Department of the Maggiore della Carità Hospital in Novara for first visit or checkup for excess weight between January 1, 2024, and May 30, 2024, of both sexes who satisfy the following inclusion criteria will be included in the study:

Inclusion criteria:

1. Ages between 6 and 17 years old;
2. BMI compatible with obesity or overweight according to IOTF criteria (6)
3. Signing of informed consent by parents/legal guardians.

Exclusion criteria:

1. Ages under 6 or over 18 years old
2. Previous diagnosis of type 2 diabetes mellitus already placed on dietary or drug therapy
3. Subjects already placed on a dieto-therapeutic regimen
4. Obesity secondary to diseases: genetic (Prader Willi syndrome, Down syndrome); metabolic and endocrine (Cushing's syndrome, hypothyroidism)

Informed Consent

After reading the study information sheet, patients will be enrolled only after signing the informed consent form by both parents or legal representative and recruited minor subjects (see patient and parent/legal guardian information sheets attached to the protocol).

Body composition measurement and dietary pattern definition

At enrollment (V1), included subjects will undergo a clinical examination as per normal practice, in which a bioimpedensiometric analysis for body composition assessment is planned. Impedenziometric analysis will be performed using a TANITA MC-780MA scale.

Following the bioimpedensiometric analysis and clinical examination, a dietary pattern based on the Mediterranean Diet will be delivered. The composition of the diet will be distributed as follows: 55-60% carbohydrates (45-50% complex carbohydrates and no more than 10% simple sugars), 25-30% lipids and 15% protein. It will be studied according to the LARN guidelines (Italian Society of Human Nutrition, 2014).

Follow-up

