Patients will be evaluated at the time of enrollment (V1), after 3 months (V3) and after 6 months (V6) as per clinical practice.

At the recruitment visit (V1), the following demographic and medical history data of the patient and family will be collected:

sex, gender, age (years), ethnicity, weight and length at birth, type and duration of breastfeeding, parents' age (years), family history of previous diseases (Arterial Hypertension, Dyslipidemia, Hepatic Steatosis, Diabetes (specify whether type I or II and oral or insulin therapy) and cardiovascular disease, parents' smoking habit, presence of maternal gestational diabetes), socioeconomic level of the household.

The following assessments will be made at all times (V1,V3,V6):

1. Anthropometric measurements

- Height
- Weight
- BMI and BMI SDS
- Growth percentile according to Cacciari curves (8)
- Waist-to-hip circumference, waist-to-height ratio
- Bioimpedance analysis
- PA and heart rate

- Tanner Stadium (9)

2. Eating habits and anamnestic characteristics

- Semi-quantitative food frequency questionnaire (24h recall)
- KIDMED Mediterranean diet adherence questionnaire (10)
- IPAQ-A Physical Activity Questionnaire

Biochemical assessments will also be performed at the beginning and end of the protocol (V1 and V6), according to normal clinical practice (baseline hematochemical tests and/or OGTT). The tests will be performed at the clinical biochemistry laboratory of the AOU “Maggiore della Carità” in Novara.

During the biochemical evaluations, two serum and two plasma samples will be taken for Asprosine, Irisin, and Ghrelin dosage to search for new markers related to obesity and its complications. The analyses will be carried out at the Laboratory of Biochemistry at Eastern Piedmont University.

The determination of clinical parameters will be performed locally at the Pediatric Auxology and Endocrinology outpatient clinic of the Pediatric Clinic of the Maggiore della Carità Hospital in Novara, while the BIA examination will be performed at the Endocrinology outpatient clinic of the Maggiore della Carità Hospital in Novara.

EXPECTED RESULTS

A change in body mass index is expected, based on the BMI z-score and an improvement in body composition 6 months after the first visit and then the implementation of the dietary pattern. In addition, an improvement in metabolic parameters (insulin resistance, glycemic intolerance, dyslipidemia, hepatic steatosis) is expected.

DATA COLLECTION AND ANALYSIS

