Data will be collected by the Principal Investigator, [name], at the outpatient clinic of Pediatric Endocrinology and Auxology at the AOU “Maggiore della Carità” in Novara and will be collected on an Excel file protected by username and password; each patient will be registered and identified by a code in order to ensure anonymity. Statistical analysis will be conducted by a Researcher from the University of Eastern Piedmont.

Calculation of sample size

Assuming a power of 80%, a first-type error of 0.05, a mean BMI z-score at V1 of 2.81, a corresponding standard deviation of 0.9 (12) a correlation between the measurements at V6 and V1 of 0.5, 70 children will be enough to be able to observe a change in BMI z-score of 0.3.

STATISTICAL ANALYSIS

Descriptive statistics will be used to summarize demographic and anamnestic characteristics, anthropometric measures, and adherence to the Mediterranean diet and physical activity at V1.

Specifically, for numeric variables the mean and standard deviation or median and interquartile range will be reported if not distributed according to a Gaussian distribution in accordance with the Shapiro-Wilks test while categorical variables will be reported as absolute and percentage frequencies. T tests for paired data will initially be used to assess the presence of variation in anthropometric measures between V6 and V1. Next, linear mixed-effects models will be used to assess the effect of Mediterranean diet adherence and time on anthropometric measures, adjusting for anthropometric measures at V1 and demographic and clinical characteristics at baseline. A random intercept will be included in the models to account for correlation of within-patient measures. The stepwise method will be used for the selection of variables to be included in the multivariable model.

All tests will be two-tailed, and the first-type error will be set at 0.05. The analyses will be performed with SAS version 9.4 (SAS Institute, Cary, NC, USA).

ETHICAL ASPECTS AND GOOD CLINICAL PRACTICE

All essential clinical records will be retained to demonstrate the validity of the study and the integrity of the data collected.

The study is designed and will be conducted according to the international and national ethical standards on biomedical research with human beings, specifically:

- *Ethical principles for medical research involving human subjects* (Declaration of Helsinki - World Medical Association, current version);

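### Stepwise selection for the adherence mixed model leaves the adherence test uncorrected for selection and can drop a weak or moderate confounder, a modest harm confined to that analysis

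*Combined protocol and SAP*

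**What the plan says.** In the STATISTICAL ANALYSIS section, paired t-tests of V6 against V1 come first. Then "linear mixed-effects models will be used to assess the effect of Mediterranean diet adherence and time on anthropometric measures". These models carry a random intercept per child, and their adjustment is described only as "adjusting for anthropometric measures at V1 and demographic and clinical characteristics at baseline". The rule for choosing the terms is: "The stepwise method will be used for the selection of variables to be included in the multivariable model". Tests are two-sided and "the first-type error will be set at 0.05".

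The section gives no candidate list, no entry or stay level, no terms that are always kept, and no allowance for the selection.

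Three other places matter:

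- PURPOSE OF THE STUDY includes, among its aims, body composition in relation to adherence to the regimen. The adherence effect is therefore something the study sets out to estimate.
- Under Follow-up, the V1 items begin with "sex, gender, age (years), ethnicity, weight and length at birth, type and duration of breastfeeding" and continue through parental age, family history, smoking, gestational diabetes and socioeconomic level. KIDMED, the adherence score, is listed among the assessments made at V1, V3 and V6.
- Under the section on body composition measurement and dietary pattern, "a dietary pattern based on the Mediterranean Diet will be delivered" at V1, after the bioimpedance analysis. The V3 and V6 scores can therefore differ from the V1 score.

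**The concern.** Every child receives the diet, and how closely each child follows it is observed, not assigned. Age, pubertal stage, physical activity and household circumstances could each relate both to adherence and to growth. Whether the adherence coefficient can be interpreted depends on adjusting for such variables.

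Stepwise selection keeps a covariate because its p-value is small, not because it confounds. With about 70 children, a covariate of weak or moderate effect often misses significance and is left out, and its effect is then partly credited to adherence. The final p-value and interval are computed as if the chosen model had been fixed in advance. Different outcomes may also end up with different adjustment sets. At stake is a false claim, or a biased estimate, for the adherence effect.

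**Working it through.** **1. The plan's own figure.** SD of the V6-V1 difference = 0.9 × sqrt(2 × (1 − 0.5)) = 0.9. n = (0.9 × (1.960 + 0.842) / 0.3)² = 70.6, against 70 in the plan. The figure reproduces. It rests on the paired comparison, so the stepwise rule does not enter it.

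**2. Size of the candidate pool.** Counting the V1 items under Follow-up: sex, gender, age, ethnicity, birth weight, birth length, breastfeeding type and duration (8), parents' age (1), five family-history conditions (5), parental smoking, gestational diabetes and socioeconomic level (3) give 17. Tanner stage, heart rate and IPAQ-A make 20. The plan speaks only of demographic and clinical characteristics, so this count is an inference.

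**3. Simulation.** The plan gives no inputs beyond N = 70, the random intercept and the 0.05 level. The rest is assumed: outcomes at V3 and V6; visit, V1 value and adherence always in the model; residual SD 1 with within-child correlation 0.7; true adherence effect 0; one confounder correlated 0.5 with adherence; forward-backward selection at 0.05 from 20 candidates. There were 3000 runs per setting (Monte Carlo SE about 0.4-0.6 points).

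| Adherence | Confounder effect (SD) | Confounder dropped | Type I error: stepwise | 5-item list with confounder | 5-item list without it | All candidates |
|---|---|---|---|---|---|---|
| Varies by visit (ICC 0.5) | 0.15 | 77% | 7.4% | 4.3% | 6.6% | 4.6% |
| | 0.25 | 48% | 8.8% | 5.3% | 10.7% | 5.3% |
| | 0.40 | 12% | 6.8% | 5.1% | 18.4% | 4.9% |
| Constant within child | 0.15 | 82% | 11.3% | 4.0% | 9.0% | 4.6% |
| | 0.25 | 53% | 14.4% | 4.6% | 18.2% | 4.5% |
| | 0.40 | 18% | 12.6% | 4.8% | 33.7% | 4.9% |

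Variants at 0.25 SD (entry level 0.15, correlation 0.3, 17 candidates, intercorrelated candidates and, for varying adherence, ICC 0.7) extend the stepwise range to 6.8-9.9% (varying) and 9.0-15.1% (constant). At correlation 0.3 alone the figures are 7.8% and 9.0%. With a covariate related to adherence but not to the outcome, so no confounding, stepwise gives 6.2% and 8.0%.

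**4. Separate runs.** A second random-intercept simulation (1200 runs per setting) gave, for varying adherence, 7.4% (0.25 SD, confounder dropped in 46%), 7.0% (0.40 SD), 6.1% (correlation 0.3) and 6.2% (no confounding). For constant adherence it gave 14.5%. All candidates gave about 4-5%. Two further child-level re-runs of the constant case at 0.25 SD gave 14.8% and 15.7%.

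**5. Hand check of the mechanism (constant adherence, 0.25 SD, confounder always omitted).** Bias = 0.25 × 0.5 = 0.125. The variance of a child's two-visit mean is (1 + 0.7)/2 = 0.85, plus the unexplained part of the confounder, 0.25² × (1 − 0.5²) = 0.047, so the SD is 0.947. SE ≈ 0.947/sqrt(62) = 0.120. The bias is then 1.04 standard errors, and a 5% test on 62 df rejects about 17.6% of the time, against 18.2% simulated.

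**6. Time effect.** With complete data its rejection rate was 4.4-5.8% under stepwise and 4.3-5.8% under a fixed model, and the two estimates differed with an SD of at most 0.004.

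**7. Adherence itself open to selection.** The stepwise sentence does not exempt adherence. In a child-level simulation (12 candidates, 2000 runs), making adherence a candidate at 0.05 meant that every reported adherence p-value was below 0.05 by construction. At 0.15, 44-63% were below 0.05 despite a null effect, with none to three confounders correlated 0.3 with adherence.

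**The case against.** The strongest reply is that the harm is small and depends on assumptions. This largely stands. No magnitude comes from the documents, and a confounder correlated 0.5 with adherence is a strong link. On the natural reading the error is 6-10%, and selection alone, without confounding, costs about one percentage point. The sample size was not based on this analysis.

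A second reply is that the plan already commits to adjusting for V1 measures and baseline characteristics. That may mean the V1 value is always kept, and the simulations grant it. It does not fix the other covariates, because the stepwise sentence decides which of them enter.

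A third reply is that a short fixed list can be worse than stepwise. This also stands: if adherence varies by visit, a list that misses the confounder gives 10.7% (0.25 SD) or 18.4% (0.40 SD), against 8.8% and 6.8%. A short list alone is therefore not a sufficient remedy.

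A reader might infer more than the documents support:

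- *The study's main before-after result or its sample size is compromised.* Neither the paired t-test nor the calculation of 70 involves the selection.
- *Inflation reaches 20-40%.* A child-level simulation with three confounders does give 21% (correlation 0.3) or 43% (correlation 0.4) at level 0.05. This needs adherence constant within child and several confounders acting in the same direction, and nothing in the documents establishes either.
- *Adherence will be a stepwise candidate.* The plan leaves this open and does not say so.

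**Conclusion.** The point holds as a modest weakness of the adherence analysis. The plan selects the model's variables in the same data and tests adherence at 0.05 with no allowance for this. If a weak or moderate confounder exists, the type I error is roughly 6-10% with adherence varying by visit and about 9-15% with adherence constant within child. It is 4-6% with the confounder or all candidates in the model.

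The mechanism is well supported: separate simulations and the hand calculation agree. The size is conditional on the assumed candidates, entry level, confounder strength and correlations. It also assumes that adherence is always in the model; if adherence is itself selected, its reported p-values are distorted further. The change is worth making because it is cheap and adherence is part of the stated aim.

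**What to change.** Replace the stepwise sentence with a pre-specified model for each anthropometric outcome. It always contains visit, KIDMED adherence (stating whether the V1 value or the value at each visit enters), the V1 value of the outcome, and baseline covariates fixed before analysis on subject-matter grounds from items already collected. Sex, age, V1 Tanner stage, V1 IPAQ-A and socioeconomic level are an example.

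Always report beside it the model with all baseline candidates and no selection. This is a required part of the change, since it guards against a list that misses a confounder. Label any stepwise search exploratory.

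Cost: plan wording and some analysis work, with no new data.

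- **Precision, adherence varying by visit.** In the simulation the all-candidate model widens the adherence SE by about 3% (ICC 0.5) to 5% (ICC 0.7) relative to the five-item list.
- **Precision, adherence constant.** Between-child df are 70 − 3 − 5 = 62 for the list and 70 − 3 − 20 = 47 for all candidates, so the ratio is sqrt(62/47) = 1.15. If Tanner stage has 5 categories and socioeconomic level 3 (assumed), each model gains 3 + 1 = 4 parameters, the df become 58 and 43, and the ratio is sqrt(58/43) = 1.16. Both models must be coded the same way for this comparison; setting 43 against 62 would overstate the cost.
- **Missing data.** The all-candidate model loses children with a missing covariate.
- **Predictor search.** Its p-values are no longer confirmatory.
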